1 BACKGROUND

1.1 Head and Neck Squamous Cell Carcinoma

Head and neck squamous cell carcinoma (HNSCC) is the eighth most common cancer in the United States with more than 53,600 new cases diagnosed annually.(1) Early-stage or locally advanced head and neck cancer patients are typically treated by a multimodality approach including surgery, radiation and chemotherapy. Mucositis-related pain and dysphagia are two of the most common primary toxicities associated with head and neck radiation. Around 80–100% of head and neck cancer patients being treated with radiation therapy suffer from oral mucositis pain. Severe mucositis (WHO grades 3 and 4) occurs in 25% of patients when standard fractionated radiation (once-daily dose) is used as a single modality. The incidence of severe mucositis can be as high as 50%–75% when radiation is used in conjunction with concurrent radio-sensitizing chemotherapy. (2, 3)

1.2 Opioid Management of Mucositis-Related Pain

Mucositis is the most common and feared side effect for head and neck cancer patients undergoing definitive radiation or chemoradiation. It is commonly clinically evident by the third week of therapy, or after approximately 30 Gy of radiation has been delivered. It may develop earlier when concomitant chemotherapy is being given or if an altered fractionation schedule is used.(4) The vast majority of patients require treatment with strong pain relief medications like morphine, fentanyl, and oxycodone as they experience moderate-to-severe mucositis-related pain. Exposure to strong opioids during radiation therapy may sometimes lead to long-term opioid dependence and adverse effects.(5, 6) Opioid naïve patients are apprehensive about using this class of drugs because of fear of habit-forming properties and drug-related side effects. As a result, this causes reduced pain medication compliance and may also contribute to poor pain control.(7, 8)

1.3 Rationale for Using Buprenorphine and Tramadol to Manage Radiation-Induced Mucositis Pain

Buprenorphine is a potent pain medication with a more favorable side effect profile and lower habit-forming potential compared to other opioids.(9, 10) It is a derivative of the thebaine, which has mixed opioid agonistic activities (agonistic effect on μ opioid and the OR L1 receptors but the antagonistic effect on kappa and delta opioid receptors).(11) Transdermal buprenorphine, with its active polymeric matrix, is superior to some of the other long-acting opioids in terms of therapeutic efficacy and compliance. Unlike other opioids, it has a ceiling effect, which means its effects increase until the person takes a certain amount; then, these effects level off, which limits euphoria, confusion, and respiratory depression.(12) Earlier studies have shown that buprenorphine suppresses opioid withdrawal and craving, and reduces illicit opioid use.(13) Furthermore, it can safely be administered with no dose adjustments in patients suffering from chronic kidney disease or those who develop chemotherapy-related acute renal failure. This unique characteristic of buprenorphine makes it a good option for mucositis-related pain control in HNSCC patients being treated with commonly used cisplatin-based chemotherapy, which is often associated with acute kidney injury.(14) With appropriate education, patients may perceive buprenorphine to be less addictive than other opioids and its use may be more acceptable. As a result, this may contribute to better pain control and compliance during treatment. Tramadol is a short-acting, weak opioid, which works by both monoaminergic and opioid mechanisms and has

synergistic activity with other long-acting opioids.(15) It is associated with lower incidence of cardiorespiratory depression and reduced dependence compared to strong opioids.

It can be used to treat breakthrough pain in combination with long-acting TD buprenorphine. Furthermore, it has been safely used in combination with both fentanyl and buprenorphine patches in earlier studies to alleviate cancer related pain.(9, 16) European studies have shown that buprenorphine patches used at higher doses (>35 µg/hour) in combination with Tylenol® or tramadol for breakthrough pain can provide adequate analgesia in cancer patients and is associated with fewer adverse effects compared to other opioids.(9) However, there is a paucity of similar studies with FDA-approved doses (5 µg to 20 µg/hour) of buprenorphine patches in the United States. In fact, to our knowledge, there are no active or completed studies of FDA-approved doses of buprenorphine in the treatment of mucositis in head and neck cancer. The goal of this study is to show efficacy of using FDA-approved doses of buprenorphine patches with oral tramadol in providing adequate pain relief in patients suffering from moderate to severe radiation-induced mucositis pain. This is an innovative and timely study question as several head and neck cancer patients continue to suffer from opioid addiction and opioid-related toxicities.

1.4 Safety data on studies using this drug combination.

Multiple studies have utilized a combination of transdermal buprenorphine and oral tramadol for cancer-related pain.(17-19). In a study by Pace et al., a group of 52 cancer patients with chronic pain were randomized 1:1 between two groups. Twenty-six patients were treated with a titratable dose of TD buprenorphine (35 µg/hour) with oral tramadol (200 mg/day) for breakthrough pain and 26 patients were treated with 60 mg/day of oral morphine. Final analysis of this study revealed that buprenorphine-based regimen was more effective in providing pain relief and was better tolerated than oral morphine. The incidence and severity of side effects were significantly lower in the buprenorphine arm compared to the morphine arm. Overall, common side effects reported in the buprenorphine arm of 26 patients were vertigo (12%), drowsiness (12%), headache (12%), constipation (8%), confusion (4%), and nausea (12%). No serious adverse event was observed.(9) In another 40-patient study of cancer patients, oral tramadol was safely used in combination with TD buprenorphine. Side effects, including nausea, buprenorphine patch insertion site pruritus and erythema, constipation, and headache were observed but were for the most part self-limiting.(18) Overall, there is some evidence in the literature to prove the safety of buprenorphine and tramadol drug combination regimen in cancer patients. However, there are no large randomized trials with this combination. Details on the dose justification of the study drug regimen are included in Section 5.2.

1.5 Symptom and Functional Assessments

Several validated metrics are available to measure treatment-related symptoms. We plan to use some of these patient-reported outcome measures and symptom and functional assessment tools in our study. We also plan to use a novel smartphone-based pain app to evaluate and monitor radiation-induced mucositis pain.

1.5.1 MD Anderson Symptom Inventory

U.S. and European phase I through IV trials have used and validated the MD Anderson Symptom Inventory (MDASI). This tool can be used in clinical and research settings. The Visual Analog Scale (0–10) measures symptom severity and interference with daily activities.(20-22) The 13-core MDASI symptom items are based on an extensive evaluation related to cancer and cancer-

treatment symptoms. MDASI symptoms include pain, fatigue, and appetite changes that the head and neck cancer population typically experiences. Patients easily complete it as a self-report tool in five minutes. Alternatively, research staff may assist patients in completing it in the clinic or by telephone with an interactive voice response system.

The instrument was developed in a manner that allows individuals to add items relevant to specific cancers and cancer treatments to patient-completed modules. The head and neck module (MDASI-HN) (21) was created with focus group input. These groups comprised head and neck cancer patients; surgical, medical, dental, and radiation oncology specialists; and symptom researchers. This instrument includes 12 to 14 head- and neck-specific items, including at least five that do not appear in the Functional Assessment of Cancer Therapy for Patients with Head and Neck Cancer (FACT-HN) — another commonly used quality of life tool. The coefficient alpha, a measure primarily used as a means of describing the reliability of multiitem scales, is highly reliable with the MDASI-HN. It was validated in a cohort of more than 200 patients in multiple studies.(3, 23) It was validated in several languages. In our trial, we plan to use the MDASI-HN tool to study the impact of radiation-induced mucositis pain on head- and neck-related symptoms and physical activity.

1.5.2 Brief Pain Inventory

The Brief Pain Inventory (BPI) asks patients to rate their pain for the last week on a 0 to 10 scale at its “worst,” “least,” “average” and “now.” The scales are presented on a 10-cm line with each number equidistant from the next. Each scale is bounded by the words “no pain” at the 0 end and “pain as bad as you can imagine” at the other. Patients are also asked to rate how pain interferes with several quality of life domains, including activity, walking, mood, sleep, work and relations with others. These scales are bounded by “does not interfere” at the 0 end and “interferes completely” at the other. Patients also are asked to estimate pain relief related to their pain treatment (by percentage), to locate areas of pain on a human figure and to estimate pain cause (cancer disease, cancer treatment, or non-cancer). The patient can complete the BPI in approximately five minutes, and the assessment is available in 12 languages.

BPI validity and reliability issues have been examined in detail.(24) In clinical trials where pain reduction (or prevention) represents primary or secondary outcome measures, professionals frequently use the BPI due to its ease of translation and brief administration. As a pain assessment tool, it is the FDA standard. The typical standard deviation for the item “worst pain” in most cancer populations is 2.4. Therefore, the finding of a one-point difference in the “worst pain” item at different times or between two comparative groups is considered significant. We plan to use the Brief Pain Inventory to assess and quantify radiation-induced mucositis pain.

1.5.3 MDASI and BPI Limitations and Rationale for the Smartphone Pain App

While the above-mentioned pain assessment tools measure oral mucositis pain, they only provide pain severity snapshots. In a head and neck cancer clinical trial, mucositis pain questionnaires are typically administered only once or twice per week. Other pain assessment tools require the patient to rate pain by memory recall of pain severity, thereby introducing a variable prone to inaccuracy.(22) Patients with severe oral mucositis experience unrelenting pain. It is often characterized by wide fluctuations with pain peaks occurring with swallowing saliva, eating, talking, and with waning analgesic medication effects. The limitation of most pain assessment tools in failing to capture fluctuating pain is well recognized. Momentary self-reporting of chronic pain with an electronic diary has been shown to overcome this limitation without undue burden.

Pain questionnaires also fail to capture patterns of pain unique to the head and neck cancer population, such as pain related to the timing of radiation (early in the week versus later in the week versus weekend). Pain, occurring at night and interfering with sleep, is likewise not accounted for in typical pain surveys for mucositis.

The difficulty of measuring radiation-induced oral mucositis pain under optimal conditions of a clinical trial is put into perspective by pointing out that in the non-research setting oncologists do not routinely use any assessment tools for measuring mucositis pain. This may be in part due to the shortcomings of the available tools described above. More likely, however, it is due to logistical restrictions — the availability of trained personnel to administer surveys, time constraints of the doctors' office schedules and the difficulty of documenting paper surveys and integrating them into the electronic medical record. Instead, most commonly, patients simply are asked to verbally report an assessment of their pain, such as worst pain level or average level of pain. The head and neck cancer patient population is predisposed to specific problems that further limit the ability to assess pain, such as the ability to articulate and accurately describe pain, language and physical communication barriers, cultural influences, as well as fear of the appearance of drug-seeking or difficult behavior.

To address the difficulty of accurately monitoring patients' mucositis pain, we developed a new method for assessing radiation-induced oral mucositis pain by adopting widely available cell phone technology.

1.5.4 Oral Mucositis (OM) Pain App

Under the auspices of an existing protocol approved by the Medical College of Wisconsin Institutional Review Board (NCT02727062), we are planning to use the OM Pain App in our study. The OM Pain App is a smartphone application that was designed to permit patients to key in pain severity, using a visual analog 0–10 scale (VAS). The app is programmed with an alarm to prompt the patient to record pain severity at prescribed intervals daily and through spontaneous patient input. Deidentified data collected on each patient's smartphone will be backed up wirelessly to cloud storage where the data can be analyzed remotely or viewed on the device. The software can generate a time-weighted measure of pain, total area under the pain curve (AUC), a summary measure that integrates serial assessments of a patient's pain over the duration of the study. The OM Pain App may be a significant improvement over the current standard of care, which is essentially nonexistent. The validated OM Pain App has the potential to significantly improve the management of pain in head and neck cancer patients. As noted, at the Medical College of Wisconsin, we developed an oral mucositis pain app (OM Pain App) and implemented a clinical trial (NCT02727062) to accurately assess pain requirements of head and neck cancer patients undergoing radiation. Preliminary data from 16 patients currently enrolled in the pain app study shows feasibility of using this application for real-time pain assessments. We are currently analyzing this data and hope to report these findings very soon. This app has potential applicability to other types of cancers in which treatment-associated pain is encountered.

1.5.5 Outcome Measure Tools to Identify Gastrointestinal, Cognitive Side Effects of the Study Regimen.

Radiation-induced mucositis pain treated with strong opioids often leads to gastrointestinal and cognitive side effects, which limit drug adherence and affect the quality of life of patients. A study by Pace et al. showed that buprenorphine is associated with lesser gastrointestinal side effects compared to other conventional opioids.(9) However, to our knowledge the gastrointestinal and

cognitive side effect profile of transdermal buprenorphine has not been studied extensively in patients being treated for mucositis pain in head and neck cancer patients. We plan to use a highly intuitive patient-reported outcome measurement information system tool called PROMIS® to assess the side effect profile of the study drug regimen. All scales of PROMIS® have been validated in cancer patients. PROMIS® is a set of person-centered outcome measures that evaluates and monitors physical, mental, and social health in adults and children. It is very sensitive, easy to use and available in multiple languages. Patients can also take assessments at home or through paper forms in clinic. Thus, there is less disruption to clinic flow with this methodology. We plan to use PROMIS® questionnaires to evaluate cognitive and gastrointestinal side effect profiles of the drug regimen and collect data to make appropriate and timely symptom-related interventions. Both PROMIS® GI and PROMIS® Cognition scores have been validated in multiple studies. (25, 26). We plan to use PROMIS® scores to evaluate the gastrointestinal and cognitive side effects of the study regimen and its impact on the quality of life of patients.

2. HYPOTHESIS, OBJECTIVES, AND ENDPOINTS

We hypothesize that the use of long-acting transdermal buprenorphine (FDA-approved dose from 5 mcg to 20 mcg/week) in conjunction with oral tramadol (50 mg to 400 mg/day) as needed for breakthrough pain will lead to a significant reduction in mucositis-related pain in locally advanced head and neck cancer patients being treated with radiation therapy by the end of treatment and the follow-up period of nine weeks.

2.1 Primary Objectives

To investigate the efficacy of using FDA-approved doses of TD buprenorphine in combination with oral tramadol to provide adequate pain control in radiation-induced mucositis.

2.2 Secondary Objectives

1. Assess compliance of the study drug regimen.
2. Assess use of off-protocol pain medications during treatment and follow-up period.
3. Compare the average weekly pain scores calculated by the pain app with the average pain scores recorded on the BPI short form.
4. Correlate average weekly pain scores with physical activity as documented on symptom and functional assessment tools, such as the MDASI-HN.
5. Assess the use of nonopioid supportive care medications (i.e., laxatives, antiemetics, and oral anesthetics) in conjunction with the study drug combination during treatment and follow-up period.
6. Assess gastrointestinal and cognitive side effect profiles of the study drug combination and their impact on cognition and quality of life.
7. Evaluate safety of the study drug combination.

2.4 Primary Endpoint

Establish the efficacy of the study regimen by showing that at least 33% of the patients will achieve at least a 30 percent decrease in the VAS pain score on the BPI questionnaire (question 3: worst pain in last 24 hours) from baseline to the end of week 9 of treatment and the follow-up period. Earlier studies have shown that the VAS pain score($\geq 4/10$) on the day of

treatment initiation may be used as the baseline in this setting and a 30% or higher reduction in the baseline pain score is a sign of a meaningful drug response.(27-29)

2.5 Secondary Endpoint(s)

1. Monitor compliance of the study drug regimen through the OM Pain App and medication diary.
2. Identify study participants who require off-protocol opioids for pain control despite being on the highest dose of the study drug combination.
3. Correlate the cumulative mean weekly pain scores calculated by the pain app with the average weekly pain scores recorded on the BPI short form.
4. Correlate the average weekly OM Pain App scores and average weekly pain scores calculated from BPI short form with head and neck symptom and functional evaluation tool MDASI-HN. The cumulative average area under the curve (AUC) weekly pain scores are expected to be inversely proportion to MDASI-HN average weekly AUC physical activity scores.
5. Maintain a weekly log of the use of other nonopioid medication, such as laxatives, antiemetics, and oral anesthetics in conjunction with the study drug combination during the treatment and follow-up period through weekly questionnaires. The average weekly use of laxatives and antiemetics is expected to decrease by the end of the follow-up period.
6. Assess the incidence and severity of gastrointestinal and cognitive side effects of the study drug regimen and their impact on the quality of life as measured by weekly PROMIS® (GI and cognition) questionnaires.
7. Safety: Assess incidence and severity of other adverse events associated with study drug combination, using the CTCAE version 5.

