8 STATISTICAL CONSIDERATIONS

8.1 Study Endpoints

8.1.1 Primary endpoint: Establish efficacy of study regimen by showing that at least 33% of patients will achieve at least a 30 percent decrease in VAS pain score from baseline to the end of week 9 of treatment and follow-up period. Earlier studies have shown that the VAS pain score ($\geq 4/10$) on the day of treatment initiation can be used as baseline in this setting and a 30% or higher reduction in baseline pain score is a sign of meaningful drug response.(27-29)

8.1.2 Secondary endpoint:

1. Monitor compliance of study drug regimen through OM Pain App and medication diary.

2. Identify study participants who require off-protocol opioids for pain control despite being on the highest dose of study drug combination.
3. Correlate cumulative mean weekly pain scores calculated by the pain app with the average weekly pain scores recorded by the BPI short form.
4. Correlate average weekly OM Pain App scores and average weekly pain scores calculated from the BPI short form with head and neck symptoms and function evaluation tool MDASI-HN. The cumulative average area under the curve (AUC) weekly pain scores are expected to be inversely proportion to MDASI-HN average weekly AUC physical activity scores.
5. Maintain a weekly log of use of other nonopioid supportive care medications, such as laxatives, antiemetics, and oral anesthetics, in conjunction with the study drug combination during treatment and follow-up period through weekly questionnaires. Average weekly use of laxatives and antiemetics is expected to decrease by the end of follow up period.
6. Assess incidence and severity of gastrointestinal and cognitive side effects of the study drug regimen and their impact on quality of life, as measured by weekly PROMIS® (GI and cognition) questionnaires.
7. Safety: Assess the incidence and severity of other adverse events associated with the study drug combination using CTCAE version 5.

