The primary analysis will compare the proportion of patients achieving a 30% drop in pain scores to the null-hypothesis value of 33% at a one-sided 5% significance level using a binomial test. The number of patients using analgesic and non-analgesic medications, as well as the occurrence of adverse events, will be tabulated and presented as counts with percentages. The average weekly pain scores, MDASI-HN, and the PROMIS® measures will be reported with descriptive statistics (mean, standard deviation, median, and range). Patient level summaries of the pain score and PRO outcomes will be created by computing area under the curve (AUC) of weekly averages. Scatterplots will be used to explore their relationship which will be quantified by Spearman's correlation coefficient. Further correlational analysis will be done by linear regression and linear fixed models.

8.7 Rationale for not Having a Stopping Rule: This is a supportive care pilot study to determine

the efficacy of transdermal buprenorphine and oral tramadol drug combination in alleviating radiation-induced mucositis pain in head and neck cancer patients. These pain medications are FDA approved and have an established safety profile. In addition to the primary efficacy endpoint, we will be evaluating other secondary end points, such as real-time pain monitoring through the OM Pain App. This will continue, even if the study drug regimen is discontinued for lack of efficacy or some other unspecified reason. This would provide us invaluable pilot data for future studies in this setting. Moreover, we have made provisions for switching to standard-of-care pain medications, such as oral oxycodone in our study for patients who don't derive adequate pain relief from the study regimen. Hence, it is reasonable to exclude a formal stopping rule for this trial.

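### Secondary objective 3 is to compare app and BPI pain scores, but the plan specifies association methods and no analysis of agreement

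*Combined protocol and SAP*

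**What the plan says.** Objective 3 in section 2.2 (and in the Protocol Summary) is to "Compare the average weekly pain scores calculated by the pain app with the average pain scores recorded on the BPI short form". The next objective in the same list uses the verb correlate, so the protocol has both words available and uses them for different objectives.

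Endpoint 3 in section 2.5 changes the verb: "Correlate the cumulative mean weekly pain scores calculated by the pain app with the average weekly pain scores recorded on the BPI short form". Section 8.1.2 repeats this almost word for word.

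For the analysis, section 8.6 says "Patient level summaries of the pain score and PRO outcomes will be created by computing area under the curve (AUC) of weekly averages", then "Scatterplots will be used to explore their relationship which will be quantified by Spearman's correlation coefficient", then "Further correlational analysis will be done by linear regression and linear fixed models". Average weekly pain scores also receive the usual descriptive statistics. Section 8.6 does not name the app and BPI as a pair. No paired difference, limits of agreement, concordance or intraclass coefficient, or agreement threshold appears in the document.

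The two scores are also built differently:
- **App:** up to four readings a day (study calendar, footnote 5), averaged by week (section 5.9.1).
- **BPI:** footnote 4 of the calendar and sections 4.8 and 4.9 attach the label average weekly to question 3. On the form in Appendix 4, question 3 asks for the worst pain of the last 24 hours, and question 5 is the weekly-average item.

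**The concern.** To compare two 0–10 pain scores is to ask whether they give the same number. A rank correlation asks only whether they order patients the same way. A coefficient near 0.9 could be reported as meeting objective 3 while one instrument reads a point or more above the other.

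Section 1.5.2 treats a one-point difference in BPI worst pain as significant, so an offset of that size matters by the protocol's own standard. Testing the clinical usefulness of the app is a stated purpose of the pilot (section 3.1), and section 2.6 proposes to use scores from both instruments to assess efficacy. A later trial planned from these data would need to know how app scores relate to BPI scores in level as well as in rank.

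**Working it through.** **The plan's own figure.** No sample size, precision or threshold is stated for the app–BPI comparison. The only powered figure is the primary design in section 8.4, which supplies n = 18. It reproduces: with 10 or more responders of 18, the exact binomial type I error at 0.33 is 0.0405 and power at 0.63 is 0.816 (stated: at least 0.80). Enrolment is 18 / (1 − 0.10) = 20.

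**Inputs.** SD = 2.4 (section 1.5.2, BPI worst pain), assumed equal for both scores. The between-instrument correlation r is not in the document; 0.5 to 0.9 is assumed. n = 18, one pair per patient.

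**Step 1: what Spearman ignores.** The coefficient uses ranks only. In one generated sample of 18 pairs it was 0.814 as drawn, 0.814 after adding 2 points to every score of one instrument, and 0.814 after halving that instrument's scores.

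**Step 2: size of the blind spot.** With equal SDs and offset b, Lin's concordance is 2r·SD² / (2·SD² + b²). For r = 0.9 and SD² = 5.76 this is 10.368 / (11.52 + b²). The simulated columns are means over 4,000 data sets of 18 pairs at r = 0.9.

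| Offset b | Concordance, formula | Concordance, simulated | Spearman, simulated |
|---|---|---|---|
| 0 | 10.368/11.52 = 0.90 | 0.88 | 0.86 |
| 1 | 10.368/12.52 = 0.83 | 0.81 | 0.86 |
| 2 | 10.368/15.52 = 0.67 | 0.65 | 0.86 |

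In the same simulations a two-sided 5% paired t-test found a 1-point offset in 96% of runs and a 2-point offset in 100%. At r = 0.7 the figures were 58% and 99%. A paired difference therefore picks up what the coefficient misses.

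**Step 3: what an agreement analysis would deliver.** The SD of the difference is s = 2.4·√(2(1 − r)). The 95% CI half-width for the mean difference is t₁₇·s/√18, with t₁₇ = 2.110. The limits of agreement are the mean difference ± 1.96·s, and the CI half-width of each limit is t₁₇·s·√(1/18 + 1.96²/34).

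| r (assumed) | s | Half-width, mean difference | Limits | Half-width, each limit |
|---|---|---|---|---|
| 0.5 | 2.40 | 1.19 | ± 4.7 | 2.1 |
| 0.7 | 1.86 | 0.92 | ± 3.6 | 1.6 |
| 0.8 | 1.52 | 0.75 | ± 3.0 | 1.3 |
| 0.9 | 1.07 | 0.53 | ± 2.1 | 0.9 |

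A mean difference of one point can be estimated usefully if r is about 0.7 or more. The limits are imprecise throughout.

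**Step 4: the planned coefficient is imprecise too.** With Fisher's z and variance (1 + ρ²/2)/(n − 3), an observed 0.7 gives z = 0.867 and standard error √(1.245/15) = 0.288. The 95% CI is about 0.29 to 0.89.

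**Step 5: is an offset plausible?** A weekly mean of momentary readings is being set against a single recalled worst value from one day. On definition alone the worst value would usually be the higher. The document gives no figure for the gap.

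**The case against.** **The plan is more than a correlation coefficient.** Section 8.6 also lists means, medians, regression and linear models. With complete pairs, the difference between the two instruments' means equals the mean paired difference, and an offset of 2 points would also show in a scatterplot or a regression intercept. This stands: a reader might infer that the plan as a whole cannot reveal an offset, and that goes too far. But section 8.6 does not say that pain scores will be tabulated by instrument. It gives no interval for a difference, specifies no app-versus-BPI model, and itself calls the models correlational.

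**The two scores are not the same quantity.** If question 3 is used, a gap is expected by definition, and Bland-Altman limits would report a difference of construct as poor agreement. This stands too. Correlation is defensible for different constructs, so the BPI item has to be settled before agreement is analysed.

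**The instruments have mostly separate roles.** A reader might infer that app and BPI scores are interchangeable for starting treatment, titration and outcome, so that an offset would distort all three. The document does not support that. Most statements of the start rule require both instruments (sections 3.2, 4.4, 5.4), dose adjustments go through the app (section 5.4), and the primary endpoint is BPI question 3 (section 2.4). Section 4.9 does attach the week 9 primary data to the app item, but that is a separate endpoint-definition question which no agreement statistic settles.

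**The stakes are small.** This is an unpowered secondary endpoint in a 20-patient pilot, and no claim of validation is attached to it. That limits the severity.

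**Conclusion.** The point holds in a limited form. The objective promises a comparison; the endpoint and section 8.6 provide association measures with no analysis of agreement. The one coefficient named is unchanged by any constant shift or rescaling of either instrument, so it cannot answer the objective. The mismatch in wording and the invariance of Spearman need no assumptions.

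The sizes do rest on assumptions: an SD of 2.4 borrowed from the worst-pain item for both scores, assumed correlations of 0.5 to 0.9, normally distributed scores in place of a bounded 0–10 scale, and one pair per patient. They illustrate the problem and do not predict this trial's result.

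Severity is low. It would be wrong to conclude that the app is inaccurate, or that titration decisions are affected. Titration turns on scores sustained for 72 or 96 hours, and neither the planned analysis nor the proposed one, both based on weekly averages, can show on which days the two instruments cross a threshold.

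**What to change.** 1. Use the same verb in objective 3 (Protocol Summary and section 2.2) and endpoint 3 (Protocol Summary, sections 2.5 and 8.1.2).
2. Name the scores to be paired: the app weekly mean with BPI question 5 for the same week. For any comparison with question 3, use the app maximum over the matching 24 hours, or label the result as a comparison of different constructs.
3. In section 8.6, prespecify the mean app-minus-BPI difference with a 95% CI and Bland-Altman limits of agreement, with variance estimates that allow for repeated weeks within a patient.
4. Keep the scatterplot and Spearman's coefficient as a supplement.
5. State that the limits are descriptive and carry no pass/fail threshold.

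The cost is a wording amendment and a little more analysis. Both instruments are already collected weekly or more often, so no new data are needed. The drawback is imprecision: with about 18 patients, SD 2.4 and an assumed correlation of 0.7, the limits span about ± 3.6 points around the mean difference, and each limit is itself uncertain by about 1.6 points. Repeated weeks add information, but less than their number suggests, because weeks within a patient are correlated.
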